5.7 Clinical investigations

Physical examination

A brief clinical examination will be conducted to eliminate features associated with decompensated cirrhosis and to measure vital signs. Vital signs will be measured at every visit, including the following: systolic and diastolic blood pressure, heart rate and temperature.

Ophthalmology examination

All patients in the interferon arm will have a baseline eye examination.

Concomitant medications

Records of all prescribed and over the counter medications will be collected at each visit.

Medical History

A history of significant previous illnesses and ongoing co-morbidities will be collected.

Fibroscan (or ARFI)

A measurement will be made at the screening visit to confirm that cirrhosis is not present.

Ultrasound

An ultrasound of the liver will be performed at the screening visit to exclude the presence of hepatocellular carcinoma.

Pregnancy test

A pregnancy test will be performed at the baseline visit for all females who are not considered to be using adequate contraception. In the interferon arm an additional pregnancy test will be performed at the visit before interferon treatment commences to ensure that patients are not pregnant before commencing treatment. Patients will be asked to use adequate contraception whilst on interferon to prevent pregnancy or for male participants to prevent pregnancy in a female partner.

Adequate birth control methods are defined as those that can achieve a failure rate of less than 1% per year when used consistently and correctly. Examples include hormonal contraception, intra uterine device, bilateral tubal occlusion, vasectomised partner, sexual abstinence. Abstinence is only acceptable if it is true abstinence in line with the preferred and usual lifestyle of the patient. Periodic abstinence such as calendar, ovulation, post-ovulation, and declaration of abstinence for the duration of exposure to IMP and withdrawal are not acceptable methods of contraception.

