4 PARTICIPANT ENTRY

4.1 Study population

Subjects for the trial will be recruited from hepatology or hepatitis specialist clinics where appropriate patients are already being monitored on treatment with nucleos(t)ide analogues. By definition these patients are strongly adherent with clinic appointments and antiviral drugs. Patients will be given a patient information sheet and invited to an appointment at least one week later.

The trial will be open to patients with HBeAg negative chronic HBV infection who have been treated with nucleos(t)ide analogues for a minimum of three years with HBV DNA < 400 IU/ml for a minimum of two years. After screening all patients will be monitored for 4 - 12 weeks to confirm they continue to meet the inclusion criteria as listed below.

(i) Inclusion criteria

- Age ≥ 18
- Chronic HBV infection
- HBeAg negative
- Nucleos(t)ide analogues treatment for ≥3 years
- HBV DNA < 400 IU/mI ≥2 years
- Informed consent

(ii) Exclusion criteria

- Cirrhosis at any time
- HBeAg to anti-HBe seroconversion within the last 3 years
- Interferon use in the last 3 years
- Contraindications to interferon use
- Participation in HBV-specific therapeutic vaccine studies within 12 months
- HCV, HDV or HIV co-infection
- Immunosuppressant use
- Contraindications to interferon use including:

- The presence of, or history of severe psychiatric condition, particularly severe depression, suicidal ideation or suicidal attempt
- Presence of or history of psoriasis
- Platelet count < 90000/mm³
- Absolute Neutrophil count < 1500/mm³
- Uncontrolled thyroid function
- Pregnancy or breastfeeding
- Women of child-bearing potential not using an effective method of contraception
- Men not using an effective method of contraception
- Clinically significant comorbidities that, in the opinion of the investigator, render the patient unsuitable.

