5 PROCEDURES AND MEASUREMENTS

The trial will be open label meaning that both patients and their medical staff will know to which arm of the trial they are randomised. All patients in the trial will discontinue nucleos(t)ide analogues at baseline with the exception of the interferon arm in the alternative protocol (see Figures 2 and 3).

Occurrence of flares which require recommencement of nucleos(t)ide analogues will be an important measure of safety and efficacy in this trial and will therefore not be counted as a withdrawal from the study. Based on the previous studies of treatment cessation it is reasonable to expect up to 45% of patients to require retreatment.

A. Control arm

Patients randomised to the control arm will discontinue their nucleos(t)ide analogue treatment at baseline. They will be followed up until 3 years after randomisation.

B. Interferon arm

Patients randomised to the Interferon arm will discontinue their nucleos(t)ide analogue treatment at randomisation. No treatment will be given for 4 weeks and then they will commence pegylated interferon 180 mcg s.c. o.w α 2a and will continue taking weekly interferon for a total of 16 weeks. They will subsequently discontinue all antiviral medications. They will be followed up until 3 years after randomisation.

Although pegylated interferon has a long list of side effects which may be both unpleasant for the patients and potentially harmful, poor adherence to treatment is not anticipated. All the centres in this study are experienced in the use of pegylated interferon for the treatment of both HBV and HCV infection and invariably achieve adherence rates over 95%.

Control and combined interferon treatment Protocol – see Figure 2

By the end of the pilot phase, if more than 40% of patients in the interferon arm experience exaggerated flares then the arm will be modified to a control and combined interferon treatment protocol in which pegylated interferon is added to the nucleos(t)ide analogue for 16 weeks from randomisation and prior to cessation of therapy rather than leaving a gap between nucleos(t)ide analogues withdrawal and pegylated interferon treatment (and compared to the control arm still). They will subsequently discontinue all antiviral medications after the 16 weeks. They will be followed up until 3 years after randomisation.

Interferon and combined interferon treatment Protocol – see Figure 3

NUC-B PROTOCOL Version 2.0 12 th Aug 2016	Sponsor Imperial College

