6 TREATMENTS

Patients in the Interferon arm (and alternative protocol interferon arms) will receive Pegylated interferon $\alpha 2a$ 180 mcg once weekly by subcutaneous injection. This is an open label study using a licensed medication in a licensed indication. Therefore the Peg-IFN will be issued on a standard hospital prescription and dispensed from standard pharmacy stock. No special labelling or packaging will be required. Storage and dispensing will be according to normal pharmacy protocols.

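### Section 5.7 restricts the baseline pregnancy test to women not on adequate contraception, so a site following it would leave most eligible women who could be pregnant untested before randomisation

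*Protocol*

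**What the plan says.** The exclusion criteria in Protocol section 4.1 include "Pregnancy or breastfeeding" and, separately, "Women of child-bearing potential not using an effective method of contraception". The word effective is not defined there.

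Section 5.7 sets the testing rule: "A pregnancy test will be performed at the baseline visit for all females who are not considered to be using adequate contraception". It continues: "In the interferon arm an additional pregnancy test will be performed at the visit before interferon treatment commences to ensure that patients are not pregnant". That second sentence carries no contraception condition. The same section defines its own term: "Adequate birth control methods are defined as those that can achieve a failure rate of less than 1% per year" under consistent and correct use, with periodic abstinence and withdrawal ruled out.

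The section 5.3 schedules mark pregnancy tests as follows, and no footnote restricts who is tested:

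- control arm: baseline only
- standard interferon arm: baseline and week 4
- alternative interferon arm: baseline only

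No schedule has a pregnancy test at screening. The eligibility check and randomisation take place at the baseline visit.

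Section 5 describes the contingent alternative regimen as one in which "pegylated interferon is added to the nucleos(t)ide analogue for 16 weeks from randomisation and prior to cessation of therapy".

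**The concern.** The baseline test is the only scheduled check on the pregnancy exclusion before randomisation. Section 5.7 reserves it for women judged not to be on adequate contraception, but 4.1 has already removed most of those who could be pregnant. The women who pass 4.1 and could still be pregnant are mainly those using contraception, and 5.7 does not send them for the test.

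Two things are at stake. The first is eligibility: a woman who is already pregnant could be randomised and, outside the alternative interferon arms, stop her nucleos(t)ide that day. Section 7.4 (viii) would later stop any interferon and encourage a return to nucleos(t)ides, while section 8.2 keeps her in the intention-to-treat population. The second is exposure: in the alternative interferon arms the first dose comes at randomisation, so a missed baseline test has no later scheduled test before dosing to make up for it.

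**Working it through.** **Who is tested.** Setting 4.1 beside 5.7, women who could conceive fall into three groups:

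- (a) No effective contraception: excluded by 4.1, yet tested under 5.7.
- (b) Adequate contraception as 5.7 defines it: eligible, not tested at baseline under 5.7.
- (c) A method accepted as effective under 4.1 but below the 5.7 standard: eligible and tested.

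Group (b) is taken to be the main eligible group that could be pregnant. The protocol gives no contraception mix, so the size of group (c) is unknown.

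**Scheduled tests for a woman in group (b).**

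| Arm | Site follows the 5.3 schedule | Site follows 5.7 literally |
|---|---|---|
| Control | 1 (baseline) | 0 |
| Standard interferon | 2 (baseline, week 4) | 1 (week 4, after randomisation) |
| Alternative interferon | 1 (baseline) | 0 or 1 |

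The last cell depends on whether the pre-interferon sentence in 5.7 extends to the alternative arms. Section 5 uses the words "with the exception of the interferon arm in the alternative protocol", which favours including them. Section 6 names the two separately: "Patients in the Interferon arm (and alternative protocol interferon arms) will receive Pegylated interferon". The 5.7 sentence also calls its test an additional one, which suggests a second test, whereas the alternative schedule has only one.

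**Expected size.** The planned total of 240 (120 per arm) and the 1% per year ceiling come from the protocol. Two inputs are assumptions: group (b) makes up 5–25% of patients, and a pregnancy goes unrecognised for 4–8 weeks.

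- Women in group (b): 0.05 × 240 = 12 to 0.25 × 240 = 60; per arm, 0.05 × 120 = 6 to 0.25 × 120 = 30.
- Expected number pregnant at randomisation = women × annual rate × weeks / 52.
- Whole trial: 12 × 0.01 × 4/52 = 0.009 to 60 × 0.01 × 8/52 = 0.092.
- Per arm: 6 × 0.01 × 4/52 = 0.005 to 30 × 0.01 × 8/52 = 0.046.

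The result scales directly with the failure rate. The 1% figure assumes consistent and correct use, and 4.1 sets no minimum time on contraception, so a conception shortly before a method was started is not counted. The protocol has no figure for either effect.

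**The case against.** The strongest reply is that the schedules already provide the test. All three tables mark it at baseline without restriction, and a site working from the table would test in every arm. A reader might infer that the control arm has no scheduled pregnancy test, or that the pregnancy exclusion is never verified. The documents do not support either: both hold only if 5.7 overrides the table. Nor is this a firm contradiction, since text may qualify a schedule mark. What remains is that 5.7 is the only place that says who is tested, and it says so restrictively, so practice could differ between sites.

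It can also be said that 5.7 is a risk-based rule, because its definition of adequate is stricter than the undefined term in 4.1, so some eligible women at higher risk are tested. That is correct for group (c), and it is why the claim is that most, not all, eligible women who could be pregnant are missed.

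A reader might further infer that interferon exposure in pregnancy is unguarded. In the standard interferon arm it is guarded by the week-4 test, and the control arm receives no interferon. The alternative arms arise only if more than 40% of a pilot arm has exaggerated flares (section 3.1), and the pre-interferon sentence may well be meant to cover them.

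Finally, the effect on the comparison is negligible. Section 5 expects up to 45% of patients to need retreatment, and section 6.5 does not count that as withdrawal. Fewer than 0.1 expected pregnancies cannot matter beside that. This stands in full.

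**Conclusion.** The point holds as a low-severity correction to eligibility checking and patient safety. The 5.7 rule, read with 4.1, mostly passes over the eligible women who could be pregnant, and it is narrower than the schedules in 5.3. The gap opens only at a site that follows 5.7. There it affects both standard arms before randomisation, with no later scheduled test in the control arm, and it matters most in the contingent alternative interferon arms, where baseline is the only scheduled test and dosing starts at once.

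On the assumed mix, 12–60 women could be randomised untested, with an expected 0.01–0.09 pregnancies in the whole trial. These figures rest on the assumed 5–25% share, the assumed 4–8 weeks and the protocol's 1% ceiling. They give no ground for inferring a threat to the primary comparison: sample size, power and analysis are unaffected. The case for the change is that the rule is misdirected and almost free to correct.

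**What to change.** Reword section 5.7 to match the 5.3 schedules: a pregnancy test at baseline, with a negative result before randomisation, for all women who could conceive, regardless of contraception. State that in the alternative interferon arms this is the required negative test before the first interferon dose. Keep the unrestricted week-4 test in the standard interferon arm.

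The cost is a small wording amendment and, measured against a literal reading of 5.7, about 12–60 more inexpensive tests on the assumed mix, at a visit that already lists the test. Measured against the 5.3 schedules it adds no tests.

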6 TREATMENTS

Patients in the Interferon arm (and alternative protocol interferon arms) will receive Pegylated interferon $\alpha 2a$ 180 mcg once weekly by subcutaneous injection. This is an open label study using a licensed medication in a licensed indication. Therefore the Peg-IFN will be issued on a standard hospital prescription and dispensed from standard pharmacy stock. No special labelling or packaging will be required. Storage and dispensing will be according to normal pharmacy protocols.

6.1 Adherence

Subjects in the Interferon arm will be monitored at visits 4,5,6,7 and 8 during the Peg-IFN treatment phase (or visits 2,4,8,12 and 16 in the alternative protocols). Adherence will be monitored by patient reporting and any dose reductions will be reported in the CRF.

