Plasma/serum storage (for virology)		х	х					Х	Х			х		Х		Х
Adverse events		х	Х	х	Х	х	Х	Х	Х	Х	х	Х	Х	Х	Х	Х
Concomitant medications	х	Х	х	Х	Х	Х	Х	Х	Х	Х	Х	х	х	Х	Х	Х
Pregnancy test		Х	Х													

Liver biopsy to be performed between screening and baseline in a sub-set of ~20 patients, 2. Baseline to occurs 4 – 12 weeks after initial screening

PROTOCOL Version 2.0 12th Aug 2016

Sponsor Imperial College

Alternative Protocol Interferon Arm

Visit number	1	2	3	4	5	6	7	8	9	10	11	12	13	14	15	16
Week	-4	0	2	4	8	12	16	20	24	28	40	52	78	104	130	156
Interferon Group	Screening ²	Baseline	IFN week 2	IFN week 4	IFN week 8	IFN week 12	IFN week 16	Post IFN week 4	Post IFN week 8	Post IFN week 12	Post IFN week 24	Post randomisation month 12	Post randomisation Month 18	Post randomisation month 24	Post randomisation month 30	Post randomisation month 36
Consent	Х															
Demographic data	х															
Inclusion / Exclusion		х														
Randomisation		х														
Medical history	х															
Vital signs	х	х	х	х	х	х	х	х	х	х	х	Х	Х	Х	Х	Х
Physical examination	х											Х		Х		Х
Liver biopsy ¹	х															
Ultrasound/Fibroscan	х															
HBV Genotyping								х								
qHBsAg	х															
HBsAg		х		х				х				Х		Х		Х
HBV DNA	х	х	х	х	х	х	х	х	х	х	х	Х	Х	Х	Х	Х
LFTs	х	х	х	х	х	х	х	х	х	х	х	Х	Х	Х	Х	Х
Thyroid function	х			Х			х				х					
Electrolytes & creatinine	Х				Х		Х			Х		х				
Prothrombin time	х	х	х	Х	х	х	х	Х	х	х	х	Х	Х	Х	Х	Х
FBC	Х		Х	Х	Х	Х	Х	Х			х	х		Х		Х
PBMC collection (for immunology assays)		х						Х		х		х		Х		Х
Plasma/serum storage (for virology)		Х						Х		Х		х		Х		Х
Adverse events		х	Х	х	х	х	х	Х	х	х	х	Х	Х	Х	Х	Х
Concomitant medications	Х	Х	Х	Х	Х	х	Х	Х	х	Х	х	х	х	Х	Х	Х
Pregnancy test		х														

1. Liver biopsy to be performed between screening and baseline in a sub-set of ~20 patients, 2. Baseline to occurs 4 – 12 weeks after initial screening

Additional visits may be made during interferon therapy to support or instruct patients but these will not be considered as study visits and will not be recorded in the study CRF.

Additional visits may be made at the discretion of the investigator for safety monitoring if hepatitis flares occur or for other safety reasons. These will be recorded in the unscheduled visit form.

Visit windows/tole	erance.

Arm	Visit	Tolerance
Interferon Arm	2	2 weeks – 3 months
(including	3-12	+/- 3 days
alternative	13-16	+/- 10 days
interferon arms)		
Withdrawal	2	2 weeks – 3 months

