5.5 Follow-up

In the control arm visits 3-6 will be used to monitor safety. In the Interferon arm visits 4 - 8 will be used to monitor and manage the side effects of interferon therapy.

Biological samples will be taken according to the relevant visit schedule in Section 5.3.

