9.1.3 Accountability

There are no requirements for accountability or shipping and destruction records for the trial as the IMP is used within its authorisation and prescribed from routine stock in the NHS. We will monitor, and record on the eCRF, patient adherence to pegylated interferon therapy as described in section 6.1 as a safety endpoint.

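### Section 6.1 lists interferon week numbers as visit numbers for the alternative regimen, so only one of its five adherence checks falls during treatment

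*Protocol*

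**What the plan says.** Section 6.1 fixes when adherence is checked. For the standard arm it states: "Subjects in the Interferon arm will be monitored at visits 4,5,6,7 and 8 during the Peg-IFN treatment phase". For the alternative regimens it adds "or visits 2,4,8,12 and 16 in the alternative protocols". The information comes from patient report, and dose reductions are entered in the CRF.

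The alternative regimens have their own schedule in section 5.3, headed "Alternative Protocol Interferon Arm". Its sixteen visits fall at "Week -4 0 2 4 8 12 16 20 24 28 40 52 78 104 130 156", and visits 3 to 9 are labelled "IFN week 2 IFN week 4 IFN week 8 IFN week 12 IFN week 16 Post IFN week 4 Post IFN week 8". Section 5 describes the treatment period of both alternative regimens in the same terms: "pegylated interferon is added to the nucleos(t)ide analogue for 16 weeks from randomisation and prior to cessation of therapy".

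Adherence to interferon is listed among the safety endpoints in section 2.4. Section 9.1.3 requires no accountability records and relies on recording "patient adherence to pegylated interferon therapy as described in section 6.1 as a safety endpoint". Section 8.2(i) admits interferon patients to the per-protocol population only if they completed at least 8 weeks of interferon.

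**The concern.** The list for the alternative regimens does not match the schedule it refers to. It also conflicts with its own sentence, which is about monitoring during the treatment phase: month 12 and month 36 cannot belong to a 16-week course.

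Section 6.1 is the only place that says how and when adherence is collected, and section 9.1.3 points back to it. If the eCRF or site instructions took the list at face value, the alternative arm would have a single on-treatment adherence record per patient, and the 8-week per-protocol threshold would fall in a long interval without a check. Under the Figure 3 design, where the combined regimen is compared with standard interferon, adherence would also be measured at different intensity in the two arms.

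**Working it through.** No formula applies beyond matching visit numbers to weeks.

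**Inputs**
- Named visits: section 6.1.
- Week and label of each visit: the standard and alternative interferon schedules in section 5.3.
- Interferon period in the alternative regimens: weeks 0 to 16 from randomisation (section 5).
- Arm sizes: 120 per arm, 25 of them from the pilot (Table 1, section 3.3).

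**Step 1: the standard arm, as a control.** Interferon starts at week 4, so interferon week = study week − 4. Visits 4, 5, 6, 7 and 8 are study weeks 6, 8, 12, 16 and 20, which are interferon weeks 2, 4, 8, 12 and 16. All five are on treatment, so this half of the sentence is correct.

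**Step 2: the alternative regimen.** Interferon starts at week 0, so interferon week = study week.

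| Visit named in 6.1 | Study week | Position in the schedule | Weeks after the course ends (week − 16) | On-treatment check? |
|---|---|---|---|---|
| 2 | 0 | Baseline | – | No: at or before the first dose |
| 4 | 4 | Interferon week 4 | – | Yes |
| 8 | 20 | 4 weeks post interferon | 4 | No |
| 12 | 52 | Month 12 | 36 | No |
| 16 | 156 | Month 36 | 140 | No |

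One of five named checks is on treatment, against five of five in the standard arm.

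**Step 3: where the numbers come from.** In the alternative schedule, interferon weeks 2, 4, 8, 12 and 16 are visits 3, 4, 5, 6 and 7. The list in section 6.1 reproduces the week numbers exactly.

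**Step 4: the gap.** After visit 4 (week 4) the next named check is visit 8 (week 20), an interval of 20 − 4 = 16 weeks. With weekly dosing from week 0, four doses (weeks 0 to 3) precede the week 4 check and 16 − 4 = 12 fall in the gap. The 8-week threshold lies inside it and would be reported 20 − 8 = 12 weeks later.

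**Step 5: patients affected.** If an arm is changed after the pilot, 120 − 25 = 95 patients would follow the alternative schedule.

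**The case against.** The best reply is that this is a slip whose intent is plain. The figures are the week labels in the schedule, the sentence speaks of the treatment phase, and a reader with both pages open would read weeks for visits. Patients still attend visits 3 to 7, where adverse events and concomitant medications are already recorded. The eCRF details sit in manuals that are not shown. The alternative schedule applies only if more than 40% of an arm has exaggerated flares in the pilot, and the affected endpoint and population are both secondary.

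Most of that stands, and it limits the consequence. It does not remove the contradiction: no other section corrects the list, and section 9.1.3 relies on it.

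Three stronger readings are tempting but not supported:
- **That section 5.5 has the same error.** It states: "In the Interferon arm visits 4 - 8 will be used to monitor and manage the side effects of interferon therapy". That names the interferon arm only. Where the protocol means to include the alternative arms it says so, as in section 6 and the visit-window table. Visits 4 to 8 are correct for the standard arm.
- **That completion of 8 weeks could not be shown, or that no record could stand in.** Patients could still report it at week 20, dose reductions go into the CRF without restriction to the named visits, and section 9.14 lists dispensing logs among retained records. These are weaker sources, since a dispensed dose is not a taken dose, but they are not nothing.
- **That visit 2 precedes the first dose.** The 16 weeks run from randomisation, so the first dose may be given at that visit. Either way there is no adherence yet to report.

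**Conclusion.** The point holds as an internal contradiction between sections 6.1 and 5.3. Four of the five adherence checks named for the alternative regimens cannot serve as on-treatment checks; the schedule's on-treatment visits are 3 to 7. Followed literally, adherence and completion of at least 8 weeks would rest largely on recall at week 20.

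The size is conditional. It is nil unless the pilot triggers an alternative regimen. If it does, about 95 post-pilot patients are affected: those in the interferon arm under Figure 2, or in the former control arm under Figure 3. The imbalance in measurement between randomised arms arises only under Figure 3, because the Figure 2 comparator receives no interferon. The primary intention-to-treat analysis is unaffected in every case.

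This rests on three assumptions: the pilot contributes 25 patients per arm and the target stays at 120; dosing is weekly from week 0; and the 8-week per-protocol rule, written for the interferon arm, carries over to the alternative regimens.

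**What to change.** In section 6.1, replace the list for the alternative protocols with visits 3, 4, 5, 6 and 7, and give the interferon weeks (2, 4, 8, 12 and 16) in brackets so that the two sections can be checked against each other. Set the eCRF adherence form for the alternative schedule to those visits.

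The cost is one wording correction and an eCRF setting. The visits already exist in the schedule, and no dose, treatment period or clinical rule changes. The correction is best in place before the pilot decision, so that an alternative regimen, if triggered, starts with the right collection points.
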